Within 10 minutes following administration of each of the 8 study procedure administrations with the Erchonia® FX-635™, the following will be recorded at the test site as outlined in the STUDY TEST BATTERY section above.

- Visual Analog Scale (VAS) Degree of Pain Rating
- Assessment Investigator’s Adverse Events Evaluation

FOLLOWING THE FINAL PROCEDURE ADMINISTRATION

In addition to the VAS pain rating recordings and the adverse events evaluation, within ten minutes of completion of the 8th and final procedure administration of the 4-week procedure administration phase of the study, the following will be recorded at the test site as outlined in the STUDY TEST BATTERY section above.

ASSESSMENT AND EVALUATION TOOLS

- Oswestry Disability Index (ODI)/Oswestry Low Back Pain Questionnaire
- Range of Motion (ROM)
- Subject Satisfaction With Study Outcome

BLINDING EFFICACY EVALUATION

- Subject Perceived Group Allocation and Rationale
- Assessment investigator Perceived Subject Group Allocation and Rationale

POST-PROCEDURE ACTIVITIES

POST-PROCEDURE EVALUATION PHASE

The post-procedure administration evaluation phase of this study will commence immediately following completion of the procedure administration phase, and will last 2 months (8 weeks).

POST-PROCEDURE EVALUATION TEST SITE VISITS AND MEASURES

There will be 2 post-procedure evaluation visits at the test site.

ONE MONTH POST-PROCEDURE EVALUATION

One month after completion of the procedure administration phase, the subject returns for a test site visit to record the following measures as per the STUDY TEST BATTERY section above.

- Visual Analog Scale (VAS) Degree of Pain Rating
- Oswestry Disability Index (ODI)/Oswestry Low Back Pain Questionnaire
- Range of Motion (ROM)
- Assessment Investigator's Adverse Events Evaluation

STUDY ENDPOINT EVALUATION: TWO MONTHS POST-PROCEDURE EVALUATION

Two months after completion of the procedure administration phase, the subject returns for a final test site evaluation visit. The two-month post-procedure evaluation visit will serve as the study endpoint evaluation visit, the evaluation point at which study success will be evaluated relative to baseline. At this visit, the following measures will be recorded as per the STUDY TEST BATTERY section above.

ASSESSMENT AND EVALUATION TOOLS

- Visual Analog Scale (VAS) Degree of Pain Rating
- Oswestry Disability Index (ODI)/Oswestry Low Back Pain Questionnaire
- Range of Motion (ROM)

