- Subject Satisfaction With Study Outcome
- Assessment Investigator's Adverse Events Evaluation

BLINDING EFFICACY EVALUATION

- Subject Perceived Group Allocation and Rationale
- Assessment investigator Perceived Subject Group Allocation and Rationale

AT-HOME POST-PROCEDURE EVALUATION PHASE MEASURES

DAILY MEASURES

The subject will continue to record all of the required information in the Subject Daily Diary, as applicable, at home, on each day of the two-month post-procedure administration phase.

WEEKLY MEASURES

At the end of each of post-procedure evaluation weeks 1, 2, 3, 5, 6, and 7, the subject will record the following in his or her home upon waking each morning, as outlined in the STUDY TEST BATTERY section above. These measures are already being recorded at the end of post-procedure weeks 4 and 8 as part of the scheduled test site visits.

- Visual Analog Scale (VAS) Degree of Pain Rating
- Oswestry Disability Index (ODI)/Oswestry Low Back Pain Questionnaire

TABLE OF SUBJECT EVENTS

The following table provides a progressive summary of subject events throughout this study.

| PRE-PROCEDURE ACTIVITIES |
|----------------------------------------------------------------------------------------------------------------------------------------------------------------------------------------------------------------------------------------------------------------------------------------------------------------------------------------------------------------------------------------------------------------------------------------------------------------------------------------------------------------------------------------------------------------------------------------------------------------------------------------------------------------------------------------------------------------------------------------------------------------------------------------------------------------------------------------------------------------------------------------------------------------------------------------------------------------------------------------------------------|

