Overall study success criteria is defined as at least a 35% difference between procedure groups, comparing the proportion of individual successes in each group. It is anticipated that about 55% of subjects in the test group will meet the individual success criteria and about 20% of subjects in the control group will meet the individual success criteria.

The clinical relevance of a 30% change in VAS score has been well previously established by FDA's Division of Surgical, Orthopedic and Restorative Devices through numerous pre-IDE reviews, the results of said studies that were subsequently used to successfully support various pain-reduction related indications for various Erchonia Corporation light therapy devices under Product Code NHN for the 510(k)s listed below over the past 8 years:

1. K101430; 06/22/10: "The MLS-AC DermaScanner™ is indicated, while using the red diodes, for adjunctive use in providing temporary relief of minor chronic neck and shoulder pain of musculoskeletal origin."
2. K100509; 06/08/10: "The Erchonia THL1 is indicated for use in providing temporary relief of minor chronic neck and shoulder pain of musculoskeletal origin."
3. K072206; 04/24/08: "The Erchonia EML Laser is indicated for the temporary reduction in post-surgery pain at 24 hours after surgery following breast augmentation surgery."
4. K050672; 06/02/05: "The Erchonia EVRL Laser is generally indicated while using the red diode for adjunctive use in providing temporary relief of minor chronic neck and shoulder pain of musculoskeletal origin."
5. K041139; 09/30/04: "The Erchonia EML Laser is indicated as an adjunct to liposuction procedures of the thighs, hips and stomach for reduction of pain associated with the recovery process."

Evaluation Time Point

The study end evaluation time point at which study success will be analyzed is at two months post-procedure evaluation relative to baseline evaluation.

The rationale and validation for the timing of the study endpoint is based a combination of factors, as follows:

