- The long-term follow-up results of the following Erchonia Corporation clinical trial that successfully supported the following FDA 510(k) clearance for market, demonstrated that while a clinically meaningful and statistically significant reduction in pain did occur over the course of the treatment administration period, the therapeutic effects prevailed, extended and intensified over the longer term, and the difference in efficacy results between active and control groups widened for chronic pain conditions.

Device: Erchonia® Allay™

510(k)#: K132940

Manufacturer: Erchonia Corporation

[figure not shown]
Device Class: Class II

Product Code: NHN

Clearance Date: 04/14/14

Indication for Use: The Erchonia® Allay™ laser is indicated as an adjunct to reducing chronic heel pain arising from plantar fasciitis.

The chart below shows the average VAS heel pain ratings for 23 subjects in the above clinical trial who had been assigned to the active device group and were followed through to 12 months post-procedure. It can be seen that while at study endpoint evaluation (2 weeks post-procedure), a statistically significant and clinically meaningful decrease in mean VAS ratings occurred, this effect prevailed through to 12 months post-procedure follow up to almost negligible recordable pain levels.

We believe this phenomenon occurs for two primary reasons:

- (i) It is hypothesized from the understanding of the general mechanism of operation of LLLT to pain reduction (as explained in detail in the clinical study protocol), that the increase in the production of ATP and activate enzymes in the underlying targeted cells of the tissue that cultivate a growth factor response within the cells and promote tissue healing, and new, healthier cell and tissue growth to strengthen and support muscles and tendons, to restore strength and flexibility and to protect against further damage, together with the anti-inflammatory properties of low level lasers that reduce nerve irritation and inflammation to provide pain relief, neither ends nor peaks at completion of treatment administration, but rather the therapeutic properties of the LLLT continue to take effect and to intensify over the prevailing weeks and months.

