- (ii) Inherent in individuals with chronic pain conditions is the hope in finding a means of substantial and durable pain relief, which is observable in the typical early onset high placebo effect attained in studies evaluating therapeutic pain relief modalities. Therefore, the need for a longer-term evaluation period in order for subjects to distinguish true and enduring pain relief from that of wishful pain relief, and for the true active therapeutic effect versus placebo to prevail is evident.

The above referenced clinical study evaluating the efficacy of Erchonia LLLT in reducing chronic heel pain arising from plantar fasciitis successfully supported the following FDA 510(k) clearance for market:

Device: Erchonia® Allay™

510(k)#: K132940

Manufacturer: Erchonia Corporation

Device Class: Class II

Product Code: NHN

Clearance Date: 04/14/14

Indication for Use: The Erchonia® Allay™ laser is indicated as an adjunct to reducing chronic heel pain arising from plantar fasciitis.

- The findings of this study are consistent with and supported by anecdotal reports by investigators in this study and of other medical professionals who regularly apply Erchonia LLLT in their practices. Many of these practitioners have reported to Erchonia Corporation that patients treated with the Erchonia laser for neck and shoulder pain and heel pain have reported anecdotally at follow-up visits many months after treatment end that their pain has continued to lessen over time.
- Further support comes from prior clinical trials by other Sponsors whose results have been successfully applied to supporting 510(k) market clearances for LLLT devices to the reduction of pain associated with chronic pain conditions. Most notable of these is the MicroLight 830 LLLT study whose results were used to support the indication of the reduction of pain associated with the musculoskeletal condition of carpal tunnel syndrome (K010175). In this study, the study evaluation endpoint was 12 weeks (3 months) post-procedure.

It is for all of the above reasons that it was decided that in the present clinical study, a longer post-procedure endpoint evaluation is warranted to attain a more accurate representation of optimal treatment effect of LLLT application with the Erchonia® FX-635™ laser device to the chronic pain condition of low back pain of musculoskeletal origin.

Hypotheses

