- **Null Hypothesis:** There will be no statistically significant difference in the proportion of individual successes, as defined, between the test and control groups.
- **Alternative Hypothesis:** There will be a statistically significant difference in the proportion of individual successes, as defined, between the test and control groups, to the effect of 35% or greater.

PRIMARY EFFICACY OUTCOME STATISTICAL EVALUATION METHODS

- **Intent to Treat (ITT) Principle:** Primary efficacy analysis will be according to the intent to treat (ITT) principle; wherein subjects will be included in the analysis if they were randomized to study procedure group, had a valid baseline (pre-procedure) visit including the required low back pain VAS recording; and received at least the first study procedure administration.
- **Missing data** will be handled through Last Observation Carried Forward (LOCF): by carrying forward the last recorded observation to fill in the subsequent missing value.
- **Per-Protocol Analysis** will also be performed for the set of all subjects who were randomized to procedure group and completed the study according to the full protocol.
- **Primary analysis of efficacy** will be according to intent to treat (ITT) analysis through the application of:
 - 1) **Fisher's exact test** to compare the proportion of success between the test and the control groups, considering that randomization has been diligently conducted and important covariates between the two groups are well balanced.
 - 2) **Parametric ANCOVA model** analysis with the mean change from baseline to study endpoint in low back pain rating on the VAS as the dependent variable, procedure group as the independent variable of interest and baseline low back pain VAS rating as a covariate. A two-tailed significance level of 5% will be considered to be statistically significant.
- **Covariates:** The following potential covariate baseline variables will be adjusted, as applicable, through application of an ANCOVA analysis for the continuous variables and linear regression analysis for categorical variables.
 - ✓ Baseline Oswestry Disability Index (ODI) score
 - ✓ Age

SUPPORTIVE SECONDARY OUTCOME MEASURE: OSWESTRY DISABILITY INDEX (ODI) SCORE

ODI scores will be considered a secondary endpoint to support the primary pain evaluation outcome measure of subject self-reported degree of low back pain levels recorded on the 0-100 Visual Analog Scale (VAS).

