The ODI score will be evaluated as follows:

- Change in ODI score from study baseline to endpoint evaluation will be calculated, with a clinically meaningful change determined to be 10% decrease in points, based on the established minimum detectable change (90% confidence) of 10% points. Statistical significance of the change will be evaluated through parametric t-test and ANCOVA analysis, with a two-way significance level of 5% considered to be statistically significant.
- Correlation analysis will be performed to evaluate the strength of the relationship between the change in VAS ratings and the corresponding change in ODI scores from baseline to study endpoint evaluation.

ADDITIONAL SUPPORTIVE OUTCOME MEASURES EVALUATION

The following additional supportive outcome measures will also be evaluated as exploratory qualitative trending of the following, without claims of statistical significance:

- a) mean changes in low back pain VAS ratings across and between all study evaluation time points, within and between procedure groups
- b) mean changes in ODI scores across and between all study evaluation time points, within and between procedure groups
- c) Mean changes in each of the range of motion measurements across and between all evaluation points, within and between procedure groups
- d) Differences in satisfaction with Study Outcome Ratings between procedure groups at both evaluated time points, and change between

EVALUATION OF RESCUE PAIN MEDICATION USE

The impact of rescue pain medication use during the study will be evaluated using descriptive statistics and qualitative comparisons.

BLINDING EFFICACY EVALUATION

Blinding efficacy evaluation will be conducted through analysis of findings from the Subject and the Assessment Investigator Perceived Subject Group Allocation and Rationale responses, recorded at completion of the four-week procedure administration phase and again at study endpoint evaluation at 2 months post-procedure administration.

Statistical evaluation of blinding efficacy will be performed as follows:

- (i) The percentage of subjects who correctly perceived their procedure group assignment and the percentage of subjects who did not correctly perceive their procedure group assignment will be calculated.

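### LOCF lets a VAS rating of any timing stand in for a missing two-month rating, and no planned analysis shows whether the success verdict depends on it

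*Combined protocol and SAP*

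**What the plan says.** All references are to the combined protocol and SAP.

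- **Endpoint.** Individual success is a VAS fall of 30% or more. The Evaluation Time Point section states: "The study end evaluation time point at which study success will be analyzed is at two months post-procedure evaluation relative to baseline evaluation".
- **Missing data.** Under Primary Efficacy Outcome Statistical Evaluation Methods, missing data "will be handled through Last Observation Carried Forward (LOCF): by carrying forward the last recorded observation to fill in the subsequent missing value". No time window, minimum follow-up or type of rating is given. Entry to the ITT set needs only randomization, a baseline VAS and one procedure. Fisher's test on the success proportions and the ANCOVA on VAS change both use that set.
- **Ratings that can be carried.** VAS is recorded "Within 10 minutes following administration of each of the 8 study procedure administrations", again at the one-month visit, and at home: "At the end of each of post-procedure evaluation weeks 1, 2, 3, 5, 6, and 7, the subject will record" it.
- **Why the endpoint is late.** The rationale cites an earlier trial of the sponsor in which "a clinically meaningful and statistically significant reduction in pain did occur over the course of the treatment administration period", but the effect then grew and "the difference in efficacy results between active and control groups widened for chronic pain conditions". It also cites a high early placebo response and "the need for a longer-term evaluation period in order for subjects to distinguish true and enduring pain relief from that of wishful pain relief".
- **Other analyses.** A per-protocol analysis covers subjects who completed the study according to the full protocol. Mean VAS change at the other time points is "exploratory qualitative trending of the following, without claims of statistical significance".
- **Success rule.** The study succeeds with a difference of at least 35 percentage points. The expected rates are about 55% and 20%.

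**The concern.** LOCF assumes that pain stays where it was when the subject was last seen. The endpoint rationale argues the opposite: early ratings mix lasting relief with a placebo response, and the active effect is still developing. A subject lost during treatment, or before the first weekly home rating, is scored on a rating taken within 10 minutes of a session. After procedure 1 alone, that is about 11 to 12 weeks before the endpoint. Later losses carry a one-month or home rating, at the latest from week 7. The documents do not say when losses are expected.

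Nothing planned shows what the carried values do. The per-protocol analysis removes the subjects in question, so it cannot show how the status assigned to them affects the result.

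What is at stake is the verdict of one small trial. Because the 35-point rule equals the planned difference, a result that goes to plan lies close to the cut-off, where a few carried ratings can decide the outcome.

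**Working it through.** **The plan's own figures.** With 55% vs 20%, two-sided 0.05, 80% power and pooled variance: n = [1.960·√(2·0.375·0.625) + 0.842·√(0.55·0.45 + 0.20·0.80)]² / 0.35² = 28.83, so 29 per arm. Dropout: 29/0.917 = 31.6, so 32. Both agree with the protocol. Its loss figure is one-twentieth in words and 8.3% in the formula; 32 minus 29 is 3 per arm (9.4%).

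**Resolution.** One subject in 32 is 3.1 points. The 35-point rule needs a gap of 12 successes (12/32 = 37.5 points), since 11/32 = 34.4 falls short.

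**Average effect.** Let m be the fraction lost in each arm and r the success rate among carried ratings. The protocol gives no r, so all values of r are assumptions.

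- LOCF rate = p(1−m) + m·r
- Missing-as-failure rate = p(1−m)

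with p = 0.55 and 0.20. Fisher power and the chance of reaching 35 points come from full enumeration of both binomials at 32 per arm. At m = 8.3%:

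| Rule (r active/control) | Difference, points | Fisher power | Chance of ≥35 points |
|---|---|---|---|
| No missing data | 35.0 | 78.3% | 47.2% |
| Missing-as-failure | 32.1 | 71.6% | 36.9% |
| LOCF, 50/50 | 32.1 | 69.5% | 37.3% |
| LOCF, 50/40 | 32.9 | 72.2% | 40.1% |
| LOCF, 52.5/35 | 33.5 | 74.1% | 42.2% |
| LOCF, 55/20 | 35.0 | 78.3% | 47.2% |

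The 52.5/35 row assumes half the losses at 50/50 and half at 55/20. At m = 5%, missing-as-failure gives 33.3 points and 74.3% power; LOCF gives 33.3 to 35.0 points and 73.2% to 78.3%.

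**A single trial, three losses per arm.** Assume 16 and 6 successes among 29 completers per arm (55% and 21%). If i active and j control carried ratings count as successes, the comparison is (16+i)/32 vs (6+j)/32, with i and j from 0 to 3, giving 16 outcomes.

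- i=0, j=0 (missing-as-failure): 31.3 points, p=0.017.
- i=0, j=3: 21.9 points, p=0.12.
- i=3, j=0: 40.6 points, p=0.002.
- Significance is lost in 3 of 16: (0,2) at 25.0 points, p=0.070; (0,3); and (1,3) at 25.0 points, p=0.074.
- The 35-point rule is met in 3 of 16: (2,0) and (3,1) at 37.5 points, and (3,0).

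Weighting by Binomial(3, r) in each arm, for example at 50/50: P(lost) = 1/8·1/2 + 3/8·1/8 = 10.9%.

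| r active/control | Loses significance | Reaches 35 points |
|---|---|---|
| 50/50 | 10.9% | 10.9% |
| 50/40 | 6.8% | 16.2% |
| 52.5/35 | 4.5% | 21.2% |
| 55/20 | 1.2% | 35.8% |

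**A single trial, one loss per arm.** Take 17 and 6 successes among 31 completers (17/31 = 55%). Missing-as-failure gives 17/32 vs 6/32: 34.4 points, and the rule is missed. One carried success in the active arm gives 18/32 vs 6/32: 37.5 points, and it is met.

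**The case against.** **Bias in favour of the device.** A reader might infer that LOCF flatters the device. The documents do not support that. If the gap between arms is smaller early on, as the endpoint rationale implies, carrying early ratings narrows the two-month difference. Unequal losses could move it either way, and no inflation of the false-positive rate has been shown.

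**Missing-as-failure as the obvious replacement.** A reader might also infer this. It does no better in the scenarios above: at 8.3% loss it ties with LOCF at 32.1 points in one and is further from the planned 35 in three. It also has the lowest chance of meeting the 35-point rule. It favours the arm with fewer losses. At 50% carried success with 8.3% lost from control only, it gives 36.7 points against 32.5 under LOCF; with losses from the active arm only, 30.4 against 34.6. This objection stands, so the choice of primary rule is a trade-off.

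**The illustration is selective.** Three losses per arm (9.4%) exceed both stated loss figures, and the 40 to 50% early control success is assumed. The results also depend on the completer counts: with 17 vs 6 and two losses per arm, no outcome loses significance (worst case p=0.039). This stands as a limit on how far the illustration can be generalised. The one-loss example, however, shows that the 35-point rule can turn on a single carried rating.

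**The per-protocol result uses no carried endpoint values.** True, but it also removes other protocol deviators and gives no range for the missing subjects.

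**A mixed model also uses early ratings.** It does, but at their own time points; it does not relabel them as the endpoint.

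**Conclusion.** The point holds as one of fragility and of a missing sensitivity analysis. The plan lets a rating of any timing serve as the two-month outcome, against its own reasons for a late endpoint, and nothing planned shows whether the verdict survives other assumptions. On average the effect is small: at 8.3% loss the expected difference falls by at most 2.9 points (35.0 to 32.1) in the scenarios tried. In a single trial a few subjects can decide it: with 16 vs 6 and three losses per arm, the chance of losing significance is 1.2% to 10.9%, and of reaching 35 points 10.9% to 35.8%.

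These figures assume the completer counts shown, equal losses in both arms and the listed carried-rating success rates, none of which the protocol states. They do not show that LOCF favours the device, nor that most losses would carry an early rating. The change should be made before unblinding; it does not call the design into question.

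**What to change.** 1. **Fisher's test and the 35-point rule.** Prespecify a tipping-point table over every possible number of successes among subjects with no two-month VAS in each arm, showing the difference, the p-value and whether the rule is met. Report missing-as-failure as a named sensitivity analysis. Whether it or LOCF is primary is the sponsor's choice, to be made knowing that at 8.3% loss missing-as-failure cuts the chance of meeting the rule from 47.2% to 36.9%, against 37.3% to 47.2% under the LOCF scenarios. The table is needed with either rule.
2. **VAS change.** Replace LOCF with a prespecified repeated-measures mixed model, adjusted for baseline VAS, with the treatment contrast at two months. Limit the visits and choose a covariance that 64 subjects can support: an unstructured one has k(k+1)/2 parameters, so 15 for 5 visits but 136 for all 16 ratings (8 post-session, 6 home, one-month and two-month). Including the rating after procedure 1 lets every ITT subject who gave it contribute. The model assumes that losses are explained by the recorded data, so keep LOCF as a sensitivity analysis.

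The cost is analysis wording and some programming, with no new data.
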